Added the following to Analysis of Secondary Endpoints: “...as well as change in NSAID/acetaminophen usage. The potential confounding effect of change in NSAID/acetaminophen usage on the treatment effect will be considered for sensitivity analysis.”	Section 10.4.3	Change was made because of new endpoint
Baseline descriptive statistics were further refined: “...and the presence of bilateral symptomatic and radiographic OA.”	Section 10.4.6	Change was made to refine baseline descriptive statistics
Sub-group analyses was revised to: “...analyzed with unilateral symptomatic OA and bilateral radiographic disease (KL grade 2-3 in both knees) subjects.”	Section 10.4.9	Change was made to refine data analyses
Changed e-mail for Medidata notification to sites	Section 10.6.1	Change was made for administrative reasons

Protocol SM04690-OA-10

Samumed, LLC

AM03V00

12 May 2020

Change	Sections Affected	Rationale
Removed Appendix 1 (Toxicity Vaccine Scale)	Appendix 1	Scale was replaced by CDISC scale for AE collection
Added Table of Changes in Amendment 01	Appendix 3	Change was made to list changes in this version
References and bibliography were updated	Throughout	Changes were made for completeness and presentation
Formatting, spelling, and grammar/terminology were refined	Throughout	Changes were made for clarity and presentation

Signature Page for VV-TMF-135008 v1.0

Reason for signing: Approved	Name: [name] Role: Vice President, Clinical Outcomes and Analytics Date of signature: 12-May-2020 18:32:48 GMT+0000
------------------------------	---

Reason for signing: Approved	Name: [name] Role: Medical Director Date of signature: 12-May-2020 18:40:02 GMT+0000
------------------------------	---

Reason for signing: Approved	Name: [name] Role: Vice President, Clinical Development Date of signature: 12-May-2020 22:02:47 GMT+0000
------------------------------	--

Signature Page for VV-TMF-135008 v1.0

10.4	Physical Examination.....	23
11.	OTHER/EXPLORATORY ANALYSIS.....	23
11.1	Sites	23
12.	MEDICATIONS	23
12.1	Concomitant Medication	23
12.2	Exposure and Compliance.....	24
12.3	NSAID/Acetaminophen Usage	24
13.	CHANGES TO PLANNED ANALYSIS	27
14.	REFERENCES.....	28
15.	APPENDICES	30
15.1	Appendix 1 – Visit Windows	30
15.2	Appendix 2 – Protocol Deviations Leading to Exclusion from Per-Protocol Analysis .	31
15.3	Appendix 3 – Estimands	34

ABBREVIATIONS

Abbreviation	Term
AE	Adverse event
ANCOVA	Analysis of covariance
AR1	Autogressive-1
ATC	Anatomical therapeutic chemical
BMI	Body mass index
CDISC	Clinical Data Interchange Standards Consortium
eCRF	Electronic case report form
EOS	End of study
eqNSAID	NSAID/Acetaminophen equivalent usage score
ET	Early termination
FAS	Full Analysis Set
IP	Investigational Product
KL	Kellgren-Lawrence
MAR	Missing-at-random
MedDRA	Medical Dictionary for Regulatory Activities
MI	Multiple imputation
mJSW	Medial joint space width
MMRM	Mixed-effects model for repeated measures
NRS	Numeric rating scale
NSAID	Nonsteroidal anti-inflammatory drug
OA	Osteoarthritis
PASS	Patient Acceptable Symptom State
Pain NRS	Weekly average of daily pain numeric rating scale
PPAS	Per-Protocol Analysis Set
RTSM	Randomization and Trial Supply Management
SAE	Serious adverse event

Abbreviation	Term
SAS	Safety Analysis Set
SD	Standard deviation
SI	International System of Units
SSQ2	Symptom Severity Question 2
WHODD	World Health Organization Drug Dictionary
WOMAC	Western Ontario and McMaster Universities Osteoarthritis Index
WOMAC Function	WOMAC physical function subscore
WOMAC Pain	WOMAC pain subscore
WPI	Widespread Pain Index

1. BACKGROUND

Osteoarthritis (OA) is the most common form of arthritis and the major cause of activity limitation and physical disability in older people. Today, 35 million people (13% of the US population) are 65 and older, and more than half of them have radiological evidence of OA in at least one joint. By 2030, 20% of Americans (about 70 million people) will have passed their 65th birthday and will be at risk for OA (Nevitt, Felson, & Lester, 2006).

The exact cause of OA is unknown, but it is associated with aging and normal wear on a joint. OA is characterized by the destruction of the articular cartilage, subchondral bone alterations, and synovitis. Patients present with pain and stiffness in their joints, with joints becoming stiffer and more immobile over time (Dougados & Hochberg, 2011). OA is a leading cause of physical disability in the US (Lawrence, et al., 2008).

Non-pharmacological management of OA (e.g., education, exercise, weight reduction) can only slightly reduce symptoms in affected joints (Bannuru, Kent, & McAlindon, 2015) (McAlindon, et al., 2014). Pharmacological management, specifically nonsteroidal anti-inflammatory drug (NSAID) use, has limited impact on clinical outcomes (Bellamy, et al., 2015) (Lapane, et al., 2015). Moreover, any clinical effects are short-lived and the potential side effects (particularly of oral NSAIDs), including but not limited to, cardiac, renal, and gastrointestinal (GI) effects, limit long-term use. Opioids are also frequently used in the management of OA pain, but have numerous potential side effects, ranging from addiction, a major public health concern in the US, to increased risk of falls, especially in the elderly.

There is a significant unmet need for pharmacological agents with disease-modifying properties for the treatment of OA. Most current treatments are designed only to relieve pain and reduce or prevent the disability caused by bone and cartilage degeneration. Available drug therapies target the symptoms, but not the cause, of this disease and no treatment inhibits or reverses the degenerative structural changes that are responsible for its (Nevitt, Felson, & Lester, 2006).

There is a need for pharmacological agents to treat OA that have disease-modifying properties, but can also provide symptom relief (decreased pain and improved function), while still being safe to use by patients with comorbid conditions or concomitant medications (Pham, et al., 2003). Such agents could also potentially delay or reduce the need for joint replacement surgery, an end-stage option which may not be suitable for OA patients in which surgical risk is deemed too high.

In order to address the need for effective pharmaceutical agents to treat OA, Biosplice has used structure-based drug design to synthesize a small molecule inhibitor of the Wnt pathway, lorecivivint (LOR; previously SM04690), as a potential OA therapeutic to be administered as a local injection in the affected joint. The Wnt pathway plays a central role in the initiation and progression of OA pathology and is crucial in normal joint metabolism (Hochberg, et al., 2012). The Wnt pathway is a major regulator of joint development and is involved in the formation of bone, cartilage, and synovium. In osteoarthritic joints, increased Wnt signaling stimulates cartilage-destroying protease production and drives local progenitor cells to become bone-forming osteoblasts instead of cartilage-forming chondrocytes, thereby contributing to

osteophyte formation and cartilage loss (Gelse, et al., 2012). Gene polymorphisms involved in Wnt signaling are associated with an increased susceptibility to OA development (Wu, et al., 2012). Established research suggests that modulation of Wnt signaling is an attractive target for the treatment of OA.

Lorecivivint inhibits the Wnt pathway through the dual inhibition of intranuclear kinases CLK2 and DYRK1A, and thereby potentially (a) reduces signs and symptoms of knee OA via an anti-inflammatory mechanism, (b) inhibits cartilage breakdown through effects on degradative enzymes, and (c) enhances formation of cartilage through effects on progenitor cells and chondrocytes residing in the joint. Thus, LOR has the potential to affect both structural and symptomatic mechanisms underlying OA. In a previous randomized controlled, 52-week Phase 2a trial, LOR demonstrated significant improvements compared with placebo in pain, function, and medial joint space width (mJSW) in subjects with moderately to severely symptomatic knee OA (Yazici, et al., 2020). In clinical studies to date, LOR has been well tolerated with a safety profile similar to that of placebo.

2. OVERVIEW

This study was a multicenter, randomized, double-blind, placebo-controlled, parallel-group study of a single dose of SM04690 injected into the target knee joint of moderately to severely symptomatic OA subjects.

3. STUDY OBJECTIVES AND ENDPOINTS

3.1 Study Objective

The objective of this study was to determine the efficacy, safety, and tolerability of the SM04690 Injectable Suspension 0.07 mg dose in the treatment of knee OA.

3.2 Study Endpoints

3.2.1 Primary Efficacy Endpoint

Change from baseline OA pain in the target knee as assessed by the weekly average of daily pain numeric rating scale (Pain NRS) at Week 12

3.2.2 Secondary Efficacy Endpoints

1. Change from baseline OA pain in the target knee as assessed by Pain NRS at Weeks 24
2. Change from baseline OA function in the target knee as assessed by Western Ontario and McMaster Universities Osteoarthritis Index (WOMAC) physical function subscore (WOMAC Function) at Weeks 12 and 24
3. Change from baseline OA disease activity as assessed by Patient Global Assessment at Weeks 12 and 24
4. Change from baseline in usage of NSAIDs and acetaminophen for target knee OA pain

3.2.3 Safety Endpoints

1. Adverse events (AEs), serious AEs (SAEs), vital signs, and clinical laboratory measures for the duration of the study

3.2.4 Other Endpoints

1. Change from baseline OA pain in the target knee as assessed by WOMAC pain subscore (WOMAC Pain) at Weeks 12 and 24
2. Change from baseline OA pain, function, and stiffness as a composite outcome measure as assessed by WOMAC Total score at Weeks 12 and 24

4. OVERALL STUDY DESIGN AND PLAN

This study was a multicenter, randomized, double-blind, placebo-controlled, parallel-group study of a single dose of SM04690 injected into the target knee joint of moderately to severely symptomatic OA subjects at Day 1.

4.1 Selection of Study Population

The study population included ambulatory males and females between 40 and 80 years of age, inclusive, with moderately to severely symptomatic knee OA. Complete inclusion/exclusion criteria are available in the study protocol.

4.2 Method of Treatment Assignment and Randomization

Subjects were randomized 1:1 (0.07 mg active per 2 mL injection:2 mL placebo) to each treatment group using Medidata Rave Randomization and Trial Supply Management (RTSM) with a permuted block design stratified by study site. 250 blocks of size 6 were generated for a total of 1500 possible subject slots.

4.3 Treatment Blinding

This was a double-blind study. As there are visual differences between the SM04690 and placebo solution, extra blinding procedures were established at each site as follows. Study medication was provided to the investigational center, which identified unblinded personnel who were able to prepare and perform the injection of study medication. Study personnel administering or preparing study medication minimized any contact with the subject following the injection and could not perform any study assessments throughout the duration of the study. Each site was required to document a blinding plan that identified the blinded and unblinded personnel at the investigational center and described how the study blind will be maintained.

4.4 Minimization of Missing Data

4.4.1 Collection of Clinical Outcomes

Clinical outcomes data were collected using electronic diary (see Protocol Section 7.3.8 for schedule of diary data collection). Eligibility criteria for the trial included successful completion of the electronic diary in the collection of both Pain NRS and WOMAC (see Inclusion Criteria 10-16). Use of electronic diary as well as enriching for subjects compliant with electronic diary use were specific protocol strategies designed to minimize the loss of key endpoint data.

4.4.2 Rescue Medication

Subjects were allowed to remain on their stable regimen of NSAIDs/acetaminophen during this study (see Protocol Section 7.8). Subjects were also allowed to change their usage as needed for pain management, including for the rescue of knee pain. Additionally, sites were instructed to

capture the amount and frequency of rescue medication use. This rescue medication policy, in addition to quantifying rescue medication use, was designed to minimize the loss of key endpoint data and provide assessment of the rescue medication's impact on key endpoint data.

4.4.3 Prohibited Medications, Treatments, and Procedures

During the conduct of the study, certain medications, treatments, and procedures were prohibited (see Protocol Section 7.6). The overall intent of these prohibitions was to minimize any possible bias in the assessment of the clinical trial endpoints. However, the protocol did allow for the use of these prohibited therapies if and only if they were required to ensure subject safety.

Investigators were instructed to notify the sponsor's Medical Monitor, who would note the prohibited therapy as a protocol deviation. These deviations were categorized as major or minor depending on the nature and timing of the interventions. Subjects were not automatically discontinued based upon prohibited therapy use, allowing for continued data collection and assessment of the impact of prohibited therapy on key endpoint data.

4.4.4 Intermittent Missing Data

Ongoing programmatic surveillance of electronic diary and visit compliance using intranet dashboards during trial conduct led to the identification of subjects that were not compliant with their electronic diary entries. Sites were notified of possible non-compliant subjects and were instructed to address any possible technical or conduct issues with these subjects prior to key endpoint data collection times. The ongoing monitoring of electronic diary compliance was a specific strategy designed to minimize the loss of key endpoint data.

5. SAMPLE SIZE DETERMINATION

A sample size of approximately 725 subjects was initially selected for this study to yield 325 evaluable subjects per treatment group assuming 10% dropout.

One thousand Monte Carlo simulations generated baseline and follow-up data from a bivariate normal distribution for each treatment group and estimated the least squares difference between treatment and placebo in an outcome's change using a baseline-adjusted analysis of covariance (ANCOVA). The proportion of statistically significant results at $\alpha = 0.05$ was estimated as the approximate power for a sample size of 325 subjects per group.

The following assumptions were made based upon observed data in the Phase 2 dose-ranging studies (SM04690-OA-02 and SM04690-OA-04):

- For Pain NRS, assuming a baseline mean (standard deviation [SD]) of 6.0 (1.5), follow-up mean (SD) of 3.0 (3.0) for SM04690 and 3.8 (3.0) for placebo (presumed treatment difference -0.8), and a baseline to follow-up correlation of 0.25, power is estimated to be 93.5%.
- For WOMAC Function, assuming a baseline mean (SD) of 60 (14), follow-up mean (SD) of 30 (29) for SM04690 and 37.5 (29) for placebo (presumed treatment difference -7.5), and a baseline to follow-up correlation of 0.25, power is estimated to be 92.0%.
- For Patient Global Assessment, assuming a baseline mean (SD) of 55 (20), follow-up mean (SD) of 35 (27) for SM04690 and 42.5 (27) for placebo (presumed treatment

difference -7.5), and a baseline to follow-up correlation of 0.25, power is estimated to be 95.3%.

Based upon a blinded evaluation of aggregate data, sample size assumptions were reassessed, and additional Monte Carlo simulations generated. A sample size of approximately 500 subjects was re-estimated for this study to yield 225 evaluable subjects per treatment group assuming 10% dropout.

- For Pain NRS, assuming a baseline mean (standard deviation [SD]) of 6.0 (1.2), follow-up mean (SD) of 3.0 (2.4) for SM04690 and 3.8 (2.4) for placebo (presumed treatment difference -0.8), and a baseline to follow-up correlation of 0.25, power is estimated to be 94.3%.
- For WOMAC Function, assuming a baseline mean (SD) of 60 (12), follow-up mean (SD) of 30 (25) for SM04690 and 37.5 (25) for placebo (presumed treatment difference -7.5), and a baseline to follow-up correlation of 0.25, power is estimated to be 89.8%.

6. ANALYSIS POPULATIONS

6.1 Full Analysis Set

The Full Analysis Set (FAS) includes all subjects who were randomized and received a study injection. The FAS is used to describe the analysis set which is as complete as possible and as close as possible to the intent-to-treat ideal of including all randomized subjects. Subjects will be analyzed as randomized for the FAS.

6.2 Per-Protocol Analysis Set

The Per-Protocol Analysis Set (PPAS) includes FAS subjects who received the correct treatment, completed the study, and did not have any protocol deviations that might impact the evaluation of efficacy outcomes (see [Section 8.2](#)). Subjects will be analyzed as randomized for the PPAS.

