4.4 END OF STUDY DEFINITION

A participant is considered to have completed the study if he or she has completed all phases of the study including the last visit shown in the Schedule of Events Table ([Section 7.3.7](#)).

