7.3.5 FINAL STUDY VISIT

Week 28 End of Study

This final study visit should occur on Day 197 with a window of \pm 7 days.

The following procedures and assessments will be performed at Week 28 (EOS):

- Collection of AE and concomitant procedures/therapies/medication data
- Review of medical history
- Assessment of NSAID/acetaminophen usage
- Physical examination, including knee examination of both knees
- Weight measurement
- Vital sign measurements (pulse rate, blood pressure, respiratory rate, and temperature)
- Venipuncture and collection of samples for clinical laboratory tests

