10.3 ANALYSIS DATASETS

Full Analysis Set (FAS): All subjects who are randomized and receive a study injection. The FAS is used to describe the analysis set which is as complete as possible and as close as possible to the intent-to-treat ideal of including all randomized subjects.

Per-Protocol Analysis Set (PPAS): FAS subjects who complete the study and do not have any major protocol deviations.

Safety Analysis Set (SAS): All subjects who receive a study injection.

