9.1 Estimands

The primary estimand for this trial is the difference between a single injection of SM04690 versus placebo in mean baseline-adjusted change in Pain NRS at Week 12, whether or not NSAIDs/acetaminophen are used (i.e. presuming a treatment policy of background NSAID and acetaminophen usage), and analyzed with MMRM, including all collected Pain NRS data in subjects in the FAS.

A summary of all estimands defined for this study is available in [Appendix 3](#).

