9.2.2 Sensitivity Analysis

The potential confounding effect of change in NSAID/acetaminophen usage on the treatment effect will be considered for sensitivity analysis, details of which can be found in [Section 12.3](#). Missing data will be imputed using the MI method for additional sensitivity analysis. The main primary analysis will also be repeated for subjects in the PPAS.

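### The per-protocol set requires completion of Week 28 even for the Week 12 sensitivity analysis, so subjects with valid Week 12 data can be excluded because of a later event

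*SAP*

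**What the plan says.** Protocol 10.3 defines the PPAS as "FAS subjects who complete the study and do not have any major protocol deviations". SAP 6.2 adds correct treatment and narrows the deviations to those bearing on efficacy, but keeps completion: it takes subjects who "completed the study, and did not have any protocol deviations that might impact the evaluation of efficacy outcomes".

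SAP 6.2 does not name a week. Protocol 4.4 does so indirectly: a participant has completed the study on having "completed all phases of the study including the last visit shown in the Schedule of Events Table". That visit is Week 28. Of it, Protocol 7.3.5 says "This final study visit should occur on Day 197 with a window of" seven days either side.

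The primary endpoint is the change from baseline in the "weekly average of daily pain numeric rating scale (Pain NRS) at Week 12". SAP 9.2.2 states "The main primary analysis will also be repeated for subjects in the PPAS", and SAP 9.3.2 says the same for the secondary analyses. Appendix 3 lists this as Sensitivity 3 for every Week 12 and Week 24 endpoint, with the PPAS as population, and asserts that this set has no missing data by definition.

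The primary estimand (SAP 9.1) uses MMRM, "including all collected Pain NRS data in subjects in the FAS".

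**The concern.** Whether a subject enters the Week 12 per-protocol analysis is decided by attendance about 16 weeks after the endpoint. Protocol 5.6.1 lists lack of efficacy and target-knee replacement among the reasons for discontinuation. Both can follow from poor pain scores at Week 12, so the set may be selected on the outcome it is meant to check.

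The usual reason for a per-protocol set, non-adherence to treatment, does not apply here. Treatment is one injection on Day 1, and SAP 7.1.2 itself notes that it cannot be removed afterwards. Leaving at Week 16 says nothing about adherence before Week 12. No NRS, WOMAC or Patient Global endpoint is set at Week 28.

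Sensitivity 3 is the only prespecified check in a different population. If it disagreed with the FAS result, a reader could not tell an effect of deviations from an effect of who stayed to Week 28.

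**Working it through.** **1. Reading the rule.** A weekly pain score needs diary entries on at least 4 of the 7 days in that week (SAP 7.3.1). Following the day pattern given there, Week 12 is Days 78 to 84. The final visit is Day 197, which is 197 − 84 = 113 days later. Two cases follow:
- A subject with 7 of 7 entries in Week 12 who leaves at Week 16 has a valid primary value and is outside the PPAS.
- A subject with 3 of 7 entries in Week 12 who attends Week 28 can be inside the PPAS with no Week 12 value.

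So the rule drops valid Week 12 data without ensuring complete Week 12 data, and the Appendix 3 statement about missing data does not follow. Appendix 3 also names only prohibited medication and NSAID/acetaminophen use as intercurrent events. Completion therefore removes subjects for a reason that the stated estimand does not cover. SAP 9.2.2 repeats the main (MMRM) model while Appendix 3 specifies ANCOVA, but the set of subjects is the same under both.

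**2. The plan's own figures (SAP 5, re-estimated).** Inputs: 225 evaluable per arm, difference 0.8, follow-up SD 2.4, correlation 0.25, two-sided alpha 0.05.
- Baseline-adjusted SD = 2.4 × √(1 − 0.25²) = 2.32.
- Power = 95.5% by formula and 95.3% by a 5,000-run ANCOVA simulation, against 94.3% stated. This is close enough to count as reproduced.
- 225 / 0.90 = 250 per arm, or 500 in total, which matches.

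**3. How many subjects.** The count is 500 × 10% × (share of dropout falling after Week 12). The share is not in the documents.

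| Share after Week 12 | Subjects |
|---|---|
| 0 | 0 |
| 25% | 12.5 |
| 16/28 (even over 28 weeks) | 28.6 |
| 75% | 37.5 |
| 100% | 50 |

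This takes 10% as total loss over 28 weeks. The SAP gives 10% only as the allowance needed to reach 225 evaluable per arm.

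**4. Precision.** Before deviation exclusions, subjects per arm with possible Week 12 data number 225 (share 0), 239 (even) or 250 (share 1). Power is 95.5%, 96.5% or 97.1%. The loss is at most 97.1 − 95.5 = 1.6 points, so precision is not the issue.

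**5. Selection.** In one arm, let a share q of those with a Week 12 value leave later, with Week 12 pain g points above that arm's mean. Removing them lowers the arm's mean by q × g / (1 − q). All q and g below are assumptions.
- Placebo 7%, active 3%, g = 2: 0.07 × 2/0.93 − 0.03 × 2/0.97 = 0.151 − 0.062 = 0.089. A true −0.8 reads as about −0.71, a shift of 0.089/0.8 = 11% towards the null.
- The same shares, g = 1: half of that, 0.044.
- Shares swapped (active 7%, placebo 3%), g = 2: −0.8 reads as about −0.89, away from the null.
- Placebo 10%, active 0%, g = 2: 0.10 × 2/0.90 = 0.222 towards the null.
- Equal q and equal g in both arms: 0.

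**The case against.** The strongest reply is that no confirmatory conclusion rests on this set. The main primary and secondary analyses use the FAS, where the subject who leaves at Week 16 keeps the Week 12 value. Sensitivity 1 stays in the FAS with multiple imputation and a tipping-point analysis. This stands, and it limits the point to a modest one.

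It can also be said that protocol and SAP agree on completion, and that one set for both time points is a deliberate choice that keeps the subjects the same. They do agree, so this is not a contradiction between the documents. But the advantage claimed in Appendix 3, a set without missing data, is not delivered.

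Third, every per-protocol set selects on post-randomisation events. That is true, and a time-point definition still loses those who leave before Week 12. It removes only the part of the selection that occurs after the endpoint and that the analysis does not need.

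Fourth, late withdrawal may be rare. Protocol 5.6.1 promises best efforts at retention, Protocol 7.8 allows rescue, and under SAP 4.4.3 prohibited therapy did not lead automatically to discontinuation. This may well keep the count low; the documents do not say.

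A reader might infer that the completion rule costs more subjects than the 26 deviation exclusions in SAP 8.2. The documents do not support that comparison. The 26 (4 + 5 + 7 + 9 + 1) is an actual count with no category for non-completion, whereas 29 is a planning figure under an assumed timing. SAP 8.2 also mentions exclusion of data as well as subjects in Appendix 2, which was not in the text available for this review. Some deviations may therefore be handled by time point. The completion condition as written still excludes the whole subject.

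**Conclusion.** The point holds for the per-protocol sensitivity analyses only. As written, the PPAS excludes compliant subjects with valid Week 12 data because of something that happened after Week 12, and that event may be related to the outcome. No text available for this review makes the completion rule specific to an endpoint. The same applies, over a shorter interval, to subjects who leave between Week 24 and Week 28.

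The number affected is between 0 and 50 of about 500, or about 29 under even dropout, if 10% is the total loss over 28 weeks. Power changes by at most 1.6 points.

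A reader might infer that the primary result is at risk, or that the per-protocol result is biased in a known direction. Neither is supported. The primary analysis uses all collected FAS data. The shift is zero when late leavers are equally common and equally different in both arms. It runs towards the null if placebo loses more subjects with high pain and reverses if active does. The 0.09-point figure illustrates one assumed pattern and is not an estimate for this trial.

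**What to change.** Define the PPAS by time point. For Week 12 endpoints, include FAS subjects who received the correct treatment, have a valid Week 12 value, and have no efficacy-relevant deviation up to Week 12. Define the Week 24 set in the same way, with Week 24 in place of Week 12. Drop Week 28 completion as a condition. The Appendix 3 statement about missing data then becomes true for an ANCOVA at each time point.

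Record the departure from Protocol 10.3 in SAP 13. If treatment codes have already been opened, report the new sets alongside the PPAS as now defined and label them as added later.

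The cost is SAP wording, two population flags, and a re-check of the blinded deviation decisions by date; no new data are needed. The PPAS would no longer be a single set of subjects, so the Week 12 and Week 24 per-protocol results would rest on slightly different people. Selection from dropout before each endpoint would remain.
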